### 6.3 Treatment Planning Guidelines and Dose Constraints

Prescription dose to PTV\_1 must cover 95% of the target volume. There are no formal coverage constraints on PTV\_2, but they should be maximized while maintaining OAR constraints at the treating physician's discretion. Recommended and mandatory dose constraints are outlined in Table 2.

Table 2. Dose Constraints Recommended for Treatment Planning

| Description      | Planning System Name | Constraints            |
|------------------|----------------------|------------------------|
| PTV_1            | PTV_1                | V33 > 95%*   |
|                  |                      |                        |
| OAR       |                      | Constraints     |
| Duodenum         | iDuodenum            |                        |
|                  |                      | V30 < 3cc*   |
|                  |                      | V35 < 1cc*   |
|                  |                      | V40 < 0.5cc* |
| Small Bowel      | iBowel               |                        |
|                  |                      | V30 < 1cc*   |
|                  |                      | V35 < 0.1cc* |
|                  |                      | V40 < 0.5cc* |
| Stomach          | iStomach             |                        |
|                  |                      | V30 < 2cc*   |
|                  |                      | V35 < 1cc*   |
|                  |                      | V40 < 0.5cc* |
| Liver            | Liver                | V12 < 50%*   |
| Combined Kidneys | Kidneys              | V12 < 75%*   |
| Spinal Cord      | Spinal_Cord          | V20 < 1cc*   |
| Spleen           | Spleen               | Mean < 2 Gy (optional) |

\* Notation indicates required mandatory constraints to be met in order to proceed with SBRT; Other constraints are recommended as reasonably achievable.

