constraints and PTV dose levels. Figure 1a illustrates a typical SBRT radiation delivery with two dose levels, GTV and a symmetric PTV expansion. Figure 1b demonstrates our novel planning technique adapted from institutional experience in escalated dose IMRT (EDR) demonstrating avoidance structures which take priority over target volumes, thus limiting OAR dose to safe volumes while allowing escalation to tumor and to TVI.

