### 6.2.1 Required Structures

- GTV: Primary pancreatic tumor as delineated on all available pre-treatment imaging and CT simulation
- iGTV: GTV expanded to encompass tumor in all phases of 4DCT or all BH scans obtained during simulation.
- iGTV\_Exp = iGTV + 3mm (uniform expansion)
- TVI: The segment of portal vein, SMV, SMA, and/or celiac artery that is in direct contact with tumor. TVI structures will be contoured to include entire radial extent of any vessel that contacts tumor. For example, the SMA TVI will include the entire 360-degree extent of SMA even if there is only 90-degree involvement of the SMA by tumor. This radial contour should extend superiorly and inferiorly on each axial slice where there is GTV contoured.
- TVI\_Exp: TVI + 3mm (uniform expansion)
- Fiducials: Fiducials and/or clips should be contoured separately starting superiorly and moving inferiorly in numeric order.
- Fiducials\_Exp: Fiducials + 3mm (uniform expansion)
- iDuodenum: Duodenum contoured to encompass tumor in all treatment phases of 4DCT or all BH scans obtained during simulation.
- PRV\_Duo: iDuodenum + 5mm (uniform expansion)
- iStomach: Stomach contoured to encompass tumor in all treatment phases of 4DCT or all BH scans obtained during simulation.
- PRV\_Stom: iStomach + 5mm (uniform expansion)
- iBowel: Any other small bowel in the treatment area, contoured to encompass tumor in all treatment phases of 4DCT or all BH scans obtained during simulation.
- PRV\_Bowel: iBowel + 5mm (uniform expansion)

- $PRV\_GI = PRV\_Duo + PRV\_Stom + PRV+Bowel$
- Bilateral kidneys, liver, spinal cord and spleen contoured per institutional guidelines. No PRV structures are required.
- Prescription Dose will be prescribed to different PTV volumes according to the dose level (figure 10):
- $PTV\_1 = iGTV\_Exp + TVI\_Exp$ . Prescription dose to this structure is 6.6Gy in 5 fractions at all dose levels to the 95% isodose line.
- $PTV\_2 = PTV1 - PRV\_GI$ . Prescription dose to this structure will be according to PTV2 dose for assigned dose level to the 95% isodose line.

Safety Note: SBRT feasibility is judged by the treating physician.

- Tumor volume is not a restrictive criteria, however, the PTV2 needs to be sufficiently covered at least 60% of the prescribed dose, while still meeting the normal tissue constraints

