- Radiological or endoscopic signs of tumor infiltration in bowel structures need to be well described before SBRT. Aside from bulging tumor masses in the bowel lumen, tumor infiltration in itself it is not an exclusion criteria but informs judgement of the physician to perform SBRT. All suspect areas need to be included in the PTV1 and sufficiently covered for at least 60% of the (6.6Gy) prescribed dose while still meeting the normal tissue constraints

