## 6.6 Compliance Criteria

### 6.6.1 Dose Uniformity

- Variation Acceptable: Minimum dose within the PTV\_1 is less than 97% of the prescribed dose, but does not fall below 93% of this dose or Maximum dose within the PTV\_1 is greater than 107% of the prescribed dose, but does not exceed 110% of this dose.
- Deviation Unacceptable: Minimum dose within the PTV\_1 is less than 93% of the prescribed dose or Maximum dose is greater than 110% of the prescribed dose.

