## **6.8 Rapid Review and Radiation Therapy Quality Assurance**

Radiation plans for all MDACC-treated patients will be reviewed at MDACC prior to treatment start during weekly gastrointestinal radiation therapy quality assurance (QA) rounds by a minimum of two gastrointestinal radiation oncology specific attending physicians who are not investigators on the trial and will also be reviewed by both radiation oncology study investigators.

To ensure protocol compliance, the treatment plans for the first three patients treated at each participating non-MDACC site will be reviewed by a MDACC Study Lead Investigator and the respective site PI. Radiation treatment plans will be reviewed to ensure a common understanding of the procedures listed in [sections 6.1](#) through [6.8](#) at the respective institution. This may be done during the trial periodically as needed.

All treatment plans will be reviewed for quality assurance according to the standard review process at each participating institution.

All plans will also be reviewed by the responsible physicist or his/her designee at each participating institution for compliance with the protocol and standard of practice at each institution.

When performed, plan reviews for patients from one institution by the staff of another institution will utilize the resources of MDACC, including WebEx; and/or other feasible resources that comply with HIPPA.

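### Section 6.6.1's 110% maximum fails every plan that delivers the PTV_2 prescription; separately, achieved PTV_2 dose, the only dose separating the levels, is not asked for beside the MTD

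*Combined protocol and SAP*

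**What the plan says.** **Dose levels.** Table 1 (Section 1.2.6) gives PTV_1 33 Gy at all three levels and PTV_2 50, 55 and 60 Gy. Table 5 (Section 12.2) ties the prior efficacy and toxicity means to PTV_2 BED. Section 6.2.1 forms PTV_2 by subtracting PRV_GI (duodenum, stomach and other small bowel, each with a 5 mm margin) from PTV_1. Of PTV_2 it says: "Prescription dose to this structure will be according to PTV2 dose for assigned dose level to the 95% isodose line".

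**Coverage.** Section 6.3 and Table 2 make V33 > 95% mandatory for PTV_1. For PTV_2, Section 6.3 states "There are no formal coverage constraints on" it and adds that "they should be maximized while maintaining OAR constraints", at the treating physician's discretion. Table 2 has no PTV_2 row. A safety note in 6.2.1 says "the PTV2 needs to be sufficiently covered at least 60% of the prescribed dose, while still meeting the normal tissue constraints". The parallel sentence for suspect bowel areas within PTV_1 reads "sufficiently covered for at least 60% of the (6.6Gy) prescribed dose while still meeting the normal tissue constraints". Section 1.2.5 describes "avoidance structures which take priority over target volumes".

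**Compliance grading.** Section 6.6.1 names only PTV_1. A maximum within PTV_1 of 107% to 110% of prescription is an acceptable variation; the unacceptable grade applies when "Maximum dose is greater than 110% of the prescribed dose" or when the PTV_1 minimum is below 93%.

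**Review and analysis.** Under Section 6.8, all lead-site plans are reviewed before treatment. For the first three patients at each other site, "Radiation treatment plans will be reviewed to ensure a common understanding of the procedures listed in" Sections 6.1 to 6.8. Every plan also has institutional QA and a physicist's compliance check. Section 12 describes dose by assigned level. Section 12.9.1 refers critical data items to a Study Manual and analysis detail to a formal SAP, neither of which was available for this review.

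**The concern.** There are two separate problems.

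The first is internal consistency. A uniformity limit suited to a single-dose target has been applied to a volume that contains a deliberate boost. If the boost is delivered, the limit is breached. A compliance grade that fails every correctly treated patient on maximum dose carries no information about plan quality.

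The second is interpretation of the MTD. The levels are 5 Gy apart in one structure, and that structure gives way when the bowel limits bind. If achieved PTV_2 dose is not shown beside the selected level, a reader planning the next trial cannot tell how distinct adjacent levels were in practice. Nor can the reader tell whether levels 2 and 3 received the BED that Section 1.2.6 regards as ablative.

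**Working it through.** **1. The plan's own figures.** BED = D × (1 + d/10), with d = D/5.

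- PTV_1: 33 × 1.66 = 54.8 (Table 1: 55).
- PTV_2: 50 × 2.0 = 100; 55 × 2.1 = 115.5; 60 × 2.2 = 132.

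All agree with Table 1.

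**2. The 6.6.1 maximum.** 1.10 × 33 = 36.3 Gy. PTV_2 is a subset of PTV_1, so the PTV_1 maximum is at least the PTV_2 maximum.

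| Level | PTV_2 prescription (Gy) | As % of 33 Gy | Highest PTV_2 maximum that passes (36.3 ÷ prescription) |
|---|---|---|---|
| 1 | 50 | 151.5% | 72.6% |
| 2 | 55 | 166.7% | 66.0% |
| 3 | 60 | 181.8% | 60.5% |

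A plan passes only if no point in PTV_2 exceeds about 60% to 73% of what was prescribed there.

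**3. The floor on PTV_2 dose, reading the 60% note as dose.** Because PTV_2 lies inside PTV_1, the 93% minimum also binds it: 0.93 × 33 = 30.69 Gy.

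| Level | 60% of prescription (Gy) | Effective floor (Gy) | BED at floor | Nominal BED |
|---|---|---|---|---|
| 1 | 30 | 30.69 | 30.69 × 1.6138 = 49.5 | 100 |
| 2 | 33 | 33 | 33 × 1.66 = 54.8 | 115.5 |
| 3 | 36 | 36 | 36 × 1.72 = 61.9 | 132 |

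V33 > 95% on PTV_1 bears on most of PTV_2 as well; 33 Gy is 66%, 60% and 55% of the three PTV_2 prescriptions.

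The note could instead mean that 60% of the PTV_2 volume must receive its prescription. The other 40% would then be held only by the PTV_1 rules. On neither reading is full PTV_2 coverage required.

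**4. Shortfall that would reach a lower level.**

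- Level 3 to nominal level 2: 1 − 55/60 = 8.3%.
- Level 3 to nominal level 1: 1 − 50/60 = 16.7%.
- Level 2 to nominal level 1: 1 − 50/55 = 9.1%.

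An equal fractional shortfall keeps the levels in order and narrows the 5 Gy gaps in proportion. For two levels to coincide, shortfall must be unequal: 60(1 − f3) = 55(1 − f2). If f2 is 0% to 10% (assumed; no figure is given), f3 must be 8.3% to 17.5%.

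**5. Would a corrected 6.6.1 work?** Against PTV_2's own prescription, 107% is 53.5, 58.85 and 64.2 Gy, and 110% is 55, 60.5 and 66 Gy. If the 95% isodose line is normalised to the plan maximum (an assumption), the maximum is 1/0.95 = 105.3% of prescription, or 52.6, 57.9 and 63.2 Gy, which meets both limits.

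The part of PTV_1 outside PTV_2 lies wholly within PRV_GI. A strict 36.3 Gy point limit there would be tighter than Table 2, which tolerates under 0.5 cc of duodenum or stomach above 40 Gy (40/33 = 121% of the PTV_1 prescription).

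**The case against.** **On 6.6.1.** The unacceptable bullet does not repeat PTV_1 beside the maximum, so its authors may have had the PTV_2 prescription in mind. But the acceptable-variation bullet does place the maximum within PTV_1, and no exemption for PTV_2 is written. The objection therefore explains the slip without removing it. A reader might go further and infer that treated patients would be excluded, or that the section cannot be used at all. The document does not support that: no section ties the grade to exclusion, dose assignment or analysis, and the 93% minimum-dose limb can still be applied.

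**On PTV_2.** Putting avoidance first and maximising target dose within bowel limits is the stated technique. The MTD is that of a prescription under fixed constraints, so analysis by nominal level is right. Plan control is also real: beyond the review and checks in 6.8, Section 6.1.1 says patients should not be treated if bowel limits cannot be met, and Section 4.4 allows discontinuation when no consensus plan is possible. All of this stands, although none of it sets a PTV_2 threshold tighter than the 60% note.

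A reader might infer that the levels collapse into one another. That is not shown. The bowel limits are fixed in Gy, so the drop to 40 Gy is 10, 15 and 20 Gy at levels 1, 2 and 3, and higher levels may be squeezed more. But 40 Gy need not be the binding limit, and no section says such a gradient is unachievable. Nor is 30 Gy a conforming minimum at level 1, since it falls below 30.69 Gy.

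**On reporting.** The SAP or Study Manual may already ask for achieved dose. The recommendation has to be conditional on that.

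**Conclusion.** The 6.6.1 maximum is wrong as written. Taken with its acceptable-variation bullet, it grades as unacceptable every plan that delivers the PTV_2 prescription at any level: 50 to 60 Gy against a limit of 36.3 Gy. This follows from the definitions of the volumes and needs no assumption about delivered dose. The consequence is a misgraded compliance measure; no primary result is shown to be affected.

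The PTV_2 point is narrower. The one dose that separates the levels has no formal coverage constraint and only one minimum that names it. On the dose reading, the effective floor is about 30.7, 33 and 36 Gy. These are bounds on what conforms, not expected doses, and the frequency of shortfall is unknown. Since 8.3% is enough to take level 3 to the nominal level 2 dose, achieved PTV_2 dose is worth reporting descriptively. This does not call the dose-finding design into question.

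**What to change.** **Section 6.6.1.** Apply the 107% and 110% maximum limits to PTV_2 against its own assigned prescription. Exempt the PTV_2 volume and its fall-off region from the PTV_1 maximum, and leave bowel dose to Table 2. Keep the 93% minimum as it is. The cost is a short wording correction.

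**Reporting.** Unless the SAP or Study Manual already requires it, take two values per patient from existing plans: PTV_2 D95 and the percentage of PTV_2 receiving the prescribed dose. For adapted courses, use the mean over delivered fractions. Report both descriptively by arm and assigned level beside the MTD. The cost is a small extraction task, somewhat larger where plans were adapted, and one added table.

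Dose assignment and the primary analysis stay by nominal level. No new PTV_2 coverage threshold is proposed, because that would change the treatment under test.

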## 6.4 Treatment Schedule

All patients will begin SBRT within 30 days of the simulation scan. If possible, treatment will begin on a Monday and complete on a Friday, unless a holiday or other treatment interruption occurs. In this case, treatments may occur on different days, but all 5 treatments must occur within an 8 day window.

## 6.5 Treatment Delivery

- Patients may be treated on any image-guided (IGRT)-enabled machine (including MRI linac).
- (on-line) adaptive planning may be done at the discretion of the treating physician if being well documented.

- Initial patient positioning will be based on MRI, CBCT, volumetric kV or CTOR imaging with shifts to referenced anatomy at the level of the tumor as appropriate.
- In case Orthogonal kV/MV, kV/kV projection, or CTOR imaging will be used to verify the location of the fiducials prior to delivery of the first treatment beam a secondary shift based on the location of fiducials should be utilized, as indicated by the position of the fiducials.
- In case MRI imaging is used for position verification, at least 2 contours need to be matched (e.g. PTV and duodenum), on-line re-contouring and planning is accepted, while well documented as serial plans given
- Documentation of active monitoring of treatment delivery accuracy will be asked using CBCT, MRI images or kV and/or MV projection imaging, either immediately before or during all (or a subset of) treatment fields.

## 6.6 Compliance Criteria

### 6.6.1 Dose Uniformity

- Variation Acceptable: Minimum dose within the PTV\_1 is less than 97% of the prescribed dose, but does not fall below 93% of this dose or Maximum dose within the PTV\_1 is greater than 107% of the prescribed dose, but does not exceed 110% of this dose.
- Deviation Unacceptable: Minimum dose within the PTV\_1 is less than 93% of the prescribed dose or Maximum dose is greater than 110% of the prescribed dose.

### 6.6.2 Volumes

- Deviation Unacceptable:
  1. Incomplete contouring of the entire GTV or PTV;
  2. Use of different margins than specified for the PTV1;
  3. Over-contouring of the GTV by > 30 cc (15 cc if it results in inclusion of extra duodenum, small intestine or stomach);
  4. Incorrect contouring of the duodenum, stomach or small intestine that results in > 15 cc overlap of the PTV with the OAR.

### 6.6.3 Treatment Interruptions

- Per protocol: All treatments occur within 8 calendar days
- Acceptable variation: All treatments occur with 8 to 16 calendar days
- Unacceptable variation: Treatments take greater than 16 days to complete

## 6.7 Definitions of Radiation related Adverse Events

The criteria used for the grading of toxicities encountered in this study are Common Toxicity Criteria (CTC) version 4.0.3

### Very likely (80-90%):

- Fatigue (which generally goes away after the radiation therapy is completed)

- Skin irritation, redness, itchiness, discomfort
- Temporary changes in blood work (decrease in blood counts, increase in liver enzymes), without symptoms

Less likely (30%):

- Nausea, vomiting (during therapy) – more common if stomach or gastrointestinal track irradiated
- Chest wall pain, rib fracture (< 10%)

Less likely, but serious (<20%):

- Gastric, esophagus, small bowel or large bowel irritation/ulceration, bleeding, fistula, obstruction or changes in motility following therapy (may require medications or surgery) (< 10% permanent changes)
- Radiation-induced liver disease (RILD) (<5%). Classic RILD is a clinical diagnosis of anicteric ascites, hepatomegaly and elevation of alkaline phosphatase relative to other transaminases that may occur 2 weeks to 3 months following radiation to the liver
- Non-classic RILD includes elevation of liver enzymes and/or any decline in liver function within 12 weeks from start of therapy (~20%). RILD can lead to liver failure that could lead to death. There is an increased risk of liver toxicity in patients with large tumors and in patients with pre-existing liver disease.
- Permanent thrombocytopenia (<1%); this may lead to bleeding
- Kidney injury (<1%); this may lead to changes on imaging and more rarely the need for medication.

## **6.8 Rapid Review and Radiation Therapy Quality Assurance**

Radiation plans for all MDACC-treated patients will be reviewed at MDACC prior to treatment start during weekly gastrointestinal radiation therapy quality assurance (QA) rounds by a minimum of two gastrointestinal radiation oncology specific attending physicians who are not investigators on the trial and will also be reviewed by both radiation oncology study investigators.

To ensure protocol compliance, the treatment plans for the first three patients treated at each participating non-MDACC site will be reviewed by a MDACC Study Lead Investigator and the respective site PI. Radiation treatment plans will be reviewed to ensure a common understanding of the procedures listed in [sections 6.1](#) through [6.8](#) at the respective institution. This may be done during the trial periodically as needed.

All treatment plans will be reviewed for quality assurance according to the standard review process at each participating institution.

All plans will also be reviewed by the responsible physicist or his/her designee at each participating institution for compliance with the protocol and standard of practice at each institution.

When performed, plan reviews for patients from one institution by the staff of another institution will utilize the resources of MDACC, including WebEx; and/or other feasible resources that comply with HIPPA.

## 7.0 STUDY DRUG MATERIALS

### 7.1 Description of Study Drug GC4419

GC4419 (avasopasem manganese) manganese, dichloro[(4aS,13aS,17aS,21aS)-1,2,3,4,4a,5,6,12,13,13a,14,15,16,17,17a,18,19,20,21a-eicosahydro-11,7-nitilo-7H-dibenzo[b,h][1,2,7,10]tetraazacycloheptadecine-κN5,κN13,κN18,κN21,κN22]-) is a water soluble, highly stable, low molecular weight manganese-containing macrocyclic ligand complex whose activity mimics that of naturally occurring SOD enzymes.

**GC4419 Administration:** 90 mg GC4419, 9 mg/mL in 26 mM sodium bicarbonate-buffered 0.9 wt. % saline for parenteral administration. There are no other excipients. GC4419 is packaged as an 11 mL ± 0.1 mL aliquot in a 10 mL amber glass vial with an S-127 4432/50 gray stopper and a 20 mm red flip-off seal.

**Placebo Administration:** Matching placebo will be prepared at the unblinded investigational site pharmacy with 100% normal saline at 250 mL, for IV administration over 60 minutes.

### 7.2 Clinical Safety Data with GC4419

In the completed Phase 1b/2a trial of GC4419 plus IMRT/cisplatin to reduce oral mucositis experience by patients with head and neck cancer, the most common adverse events observed were nausea, fatigue, dysgeusia, oropharyngeal pain, decreased white blood cell count, constipation, dry mouth, anemia, vomiting, diarrhea, decreased lymphocyte count, and decreased appetite. These and other adverse events observed are characteristic of the cisplatin/IMRT regimen in this patient population.

The following mild to moderate adverse events were reported as possibly related to GC4419 for >10% of patients in the GT-001 study: nausea, vomiting, dry mouth, diarrhea, fatigue, dyspepsia, gastroesophageal reflux disease, dizziness, dysgeusia, weight loss, decreased appetite, headache, paresthesia, and hiccups.

The following more severe adverse events were reported by treating investigators as possibly related to GC4419 in the GT-001 study: anemia, nausea, vomiting, gastroenteritis, low white blood cell count, low neutrophil count, weight loss, decreased appetite, arthritis, and reduced range of motion.

Potentially mechanism-related facial tingling or paresthesia, possibly due to nitric oxide potentiation, was reported for several patients in the GT-001 study and appears related to GC4419 dose, occurring in 11/19 (58%) patients receiving 112 mg per dose, 5/9 (55%) patients receiving 90 mg/dose, but only 2/18 (11%) at lower doses. This facial tingling/paresthesia was mild to moderate, and when it occurred it did so during GC4419 infusion with resolution shortly after the end of the infusion. It was neither treatment-limiting nor troublesome to patients, and does not pose a meaningful safety risk.

Twenty-three (50%) patients experienced at least 1 serious adverse event (SAE). SAEs reported for > 1 patient included pyrexia and vomiting (each 11%), febrile neutropenia (9%), nausea (7%), and dehydration (4%). Of the 3 patients with nausea reported as an SAE, nausea was

accompanied by vomiting in all 3 cases. Two patients, both at the 112 mg/dose level, experienced at least 1 SAE that was considered by the Investigator to be GC4419-related, including Grade 3 gastroenteritis in 1 patient and Grade 3 nausea, vomiting, and hyponatremia in other patients; these events also were considered DLTs. All other SAEs reported were considered by the Investigator to be unrelated to GC4419.

In the randomized, double-blind, placebo-controlled Phase 2b trial, GT-201, the safety profile of GC4419 was similar to that of placebo, indicating that GC4419 did not appear to add significant risk to the known toxicity of the underlying chemoradiotherapy regimen used for patients with HNC in that trial.

